To recruit a professional interpreter, we will work with the UW Health interpreter services to identify and recruit professional interpreters, and we will send a recruitment flyer through email to all Hmong interpreters and ask them to contact interpreter services if they will participate. Interpreter services will then prioritize interpreters willing to participate in the study with consenting patients (see letter of support).

Study Procedures and Interventions:

We will follow IRB guidelines on how to obtain consent remotely.

To pilot the pain assessment InfoViz tool among LEP Hmong patients in primary care.

The goal is to obtain information about the feasibility of the study protocol and identify modifications (e.g., study procedures, outcome variables) needed for the design of a larger efficacy study, consistent with the goals of a pilot study. Data will be collected from LEP Hmong patients, interpreters, and providers. We will use the same inclusion criteria for LEP Hmong patients, interpreters, and providers as previously stated. Based on a preliminary survey of patient populations served at the UW Northeast Clinic, we identified 482 LEP Hmong patients who had been seen within the past 5 years. The total number of subjects will be 50 triads of patients, interpreters, and providers. We have selected a sample size of $N = 50$ triads, which is described in the literature as sufficient for pilot evaluations.

The following are the surveys and interviews we will use.

- 1) The MUS will be used to assess MU between the patient, interpreter, and provider about pain location and quality. Specifically, we will use the main symptom item of the MUS subscale. The MUS is validated by a multiethnic and multidisciplinary expert panel using a nominal group technique. Because the MUS was developed to assess communication in general, we will adapt it to assess pain communication specifically. Also, the MUS was not developed for interpreters, so we will adapt it to include all members of the triad. We will consult with [name], a survey expert, on all the adaptations of existing measures.
- 2) Pain relief will be measured using a 5-point Verbal Rating Scale (i.e., none, slight, moderate, lots, complete) to rate pain reduction since the clinic visit. Self-reporting is appropriate as pain is a subjective experience. The Verbal Rating Scale is a gold standard for reporting pain and is documented as preferred by less-educated individuals.

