To pilot the pain assessment InfoViz tool among LEP Hmong patients in primary care, the following are our study procedures. The LEP Hmong patients, interpreters, and providers will be recruited differently. To recruit LEP Hmong patients, we will work with the Clinical Research Data Service (CRDS) at the UW–Madison Institute for Clinical and Translational Research to obtain a weekly report containing the contact information of any Hmong patients who identify as LEP and have upcoming appointments at the UW Family Medicine clinics. We will conduct telephone screening to recruit eligible participants and discuss the study's purpose. If an LEP Hmong patient agrees to participate in the study, we will obtain oral consent via phone. We will audio record the telephone screening process.

1. Prior to the visit, we will email the provider to notify him/ her about the upcoming appointment that our study team will observe. We will also email or text the interpreter based on his/her preference of communication.
2. Arrival at Clinic. Upon a patient and interpreter's arrival at the clinic, the receptionist at the front desk will direct them to the study team prior to the medical consultation with their health care providers. For the usual care phase, the patient and interpreter will continue as normal in the waiting room. For the intervention phase, we will ask the interpreter and

patient to complete the pain assessment InfoViz tool together in the waiting area, a common practice in primary care. Acknowledging potential privacy issues related to this approach, we will encourage participants to sit in areas with fewer people. The RA will observe patient-interpreter-provider interactions in both usual and intervention conditions.

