3. During Clinic Visit. For the “usual care” phase, interpreters will continue to interpret as they normally would, with verbal interpretation for patients and providers. For the “intervention” phase, the interpreter will use the pain assessment InfoViz tool with verbal descriptions of pain information. Specifically, during pain assessments, the health care providers will ask questions related to pain, including pain severity, location, and quality. When the providers ask such questions, the interpreter will use the pain assessment InfoViz tool to facilitate the communication of the Hmong patients’ pain location and quality responses. For example, when the provider asks the patient, “Tell me where your pain is located,” the interpreter will interpret the patient’s response with verbal descriptions and show the patient’s marked pain location to providers during communication between patients and providers. When the provider asks the patient, “How would you describe your pain?” and if the patient says “It hurts like a chicken pecking” in the Hmong language, the interpreter will look at the tool to identify the corresponding meaning represented in the English medical terminology and translate the patient’s pain description using this terminology to the provider. When the provider asks the patient “How would you rate your pain?”, if the patient points to the very pale face on the far right, the interpreter will state “10.” The RA will repeat the fidelity checklist to assess the interpreters’ use of the pain assessment InfoViz tool. We will audio record the conversation of the patient, interpreter, and providers during the clinical visit for both the usual care and intervention phases.

4. Post-Visit. Immediately after the clinic visit, all the participants (usual care and intervention conditions) will complete the mutual understanding scale (MUS), and answer questions about communication quality, communication satisfaction, and the demographic survey. Patients in both the usual care and intervention conditions will also orally report their pain interference to the RA. Patients and interpreters will complete the acculturation scale. Interpreters and providers will complete all the surveys in writing. All

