the participants will also answer three open-ended debriefing questions to further understand the impact of the tool on their MU, satisfaction, and acceptability of the tool. Providers will also be asked to answer two additional questions about their ability to make a pain diagnosis and prescribe appropriate pain treatment in the survey. Patients will complete the surveys orally with the RA and will be audio-recorded. The RA will collect the surveys and complete patient pain assessment InfoViz tools in person at the clinic. Within 4 weeks of the clinic visit (the recommended follow-up period for pain by clinic providers), the RA will contact patients by telephone to orally rate their pain relief, pain interference, and share whether they used the recommended pain treatments (adherence to medication). This conversation will be audio-recorded. After each data collection point, the RA will document the challenges related to attending clinic appointments (i.e., schedule changes, participants changing their minds about study staff observing the patient-provider interaction). The debriefing interviews will provide insight into the mechanisms of intervention effects and ways to enhance the implementation of the intervention and select appropriate outcomes in planning for the larger trial. After the completion of the study, we will also conduct a debriefing interview with the interpreters to better understand their experience and how we can better implement the tool in future studies.

We will also review patients' records to determine if providers are documenting patients' pain information more effectively in the absence and during the use of the pain InfoViz assessment tool.

Outcome Measures:

Type	Name	Time Frame	Brief Description
Primary	Feasibility 1. Recruitment and retention 2. Completeness of InfoViz tool 3. Fidelity of InfoViz tool use	1. Throughout the study conduct 2. Immediately post-intervention 3. Immediately post-intervention	1. Proportion of eligible participants enrolled; proportion of enrolled participants who complete the study

			
 2. Proportion of InfoViz tools with pain severity marked, at least one pain location marked, and at least one pain quality marked on the InfoViz tool. 3. Proportion of items correctly performed on the investigator designed fidelity checklist.

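### Do the primary feasibility rates, worded per participant, overstate enrolment and retention when the study unit is the triad?

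*Protocol*

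**What the plan says.** In the Outcome Measures table, the first primary feasibility item is "Proportion of eligible participants enrolled; proportion of enrolled participants who complete the study". The table does not say whether a participant is a patient, any member of a triad, or the triad itself, and it does not define completion. No target or progression threshold is attached.

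Other parts of the protocol bear on how this is read:

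- Study Procedures and Interventions: "The total number of subjects will be 50 triads of patients, interpreters, and providers". The size is justified as one "which is described in the literature as sufficient for pilot evaluations", with no expected enrolment or dropout rate.
- Recruitment Plan and Research Procedures, in the text on recruiting patients: "We will conduct telephone screening to recruit eligible participants".
- Research Procedures, step 4 (Post-Visit): "all the participants (usual care and intervention conditions) will complete the mutual understanding scale (MUS". Here the word covers all three roles.
- The same step, on the 4-week follow-up: "the RA will contact patients by telephone to orally rate their pain relief, pain interference". This call is for patients only.
- Recruitment Plan, on professional interpreters: "Interpreter services will then prioritize interpreters willing to participate in the study with consenting patients".
- Research Procedures, step 4, on later contact: "we will also conduct a debriefing interview with the interpreters to better understand their experience". The interview is placed after the study is complete.

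**The concern.** The planned unit is a triad, but the rate is worded per person. If all three roles go into one numerator and one denominator, two distortions are possible. Interpreters and providers have their study surveys at the visit and no 4-week call, so they would tend to count as completers and pull retention up. Enrolment averaged over roles could also sit well above the share of approached patients who end in a complete triad, because a triad needs all three to agree.

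The pilot exists to inform a larger efficacy study. An inflated enrolment rate would understate how many patients must be approached per triad. An inflated retention rate would understate how many patients will lack the 4-week pain relief and pain interference outcomes.

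**Working it through.** The protocol gives no rates, so there is no figure of its own to reproduce beyond the 50 triads. Every rate below is an assumption.

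**Retention, if roles are pooled.** Let p be the share of the 50 patients reached at 4 weeks, and let I and P be the numbers of distinct interpreters and providers, all assumed to complete at the visit. Pooled retention = (50p + I + P)/(50 + I + P).

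| Assumed p | I = 50, P = 50 | I = 25, P = 15 | I = 10, P = 10 |
|---|---|---|---|
| 60% | 86.7% | 77.8% | 71.4% |
| 70% | 90.0% | 83.3% | 78.6% |
| 80% | 93.3% | 88.9% | 85.7% |
| 90% | 96.7% | 94.4% | 92.9% |

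Under these assumptions pooling always raises the figure when p is below 100%, and it does so less when a few interpreters and providers serve many triads. If the interpreter debriefing counted towards completion, the direction could reverse: patients 80%, interpreters 40% and providers 100% give (0.80 + 0.40 + 1.00)/3 = 73.3%.

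**Retention, if participants means patients.** There is nothing to pool. With 40 of 50 reached, the rate is 80% (Wilson 95% interval 67.0% to 88.8%).

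**Enrolment, equal denominators and independent agreement.** Role rates of 60%, 80% and 90% average (0.60 + 0.80 + 0.90)/3 = 76.7%, while complete triads form in 0.60 × 0.80 × 0.90 = 43.2% of cases. At 80% in every role the triad rate is 0.80³ = 51.2%.

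The recruitment described is neither independent nor on equal denominators. Family interpreters are approached only after the patient is willing, and the patient names them. Professional interpreters who have already agreed are steered to consenting patients. Providers are approached through a staff meeting and an email, not once per appointment. Multiplying role rates does not model this process.

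**Enrolment, distinct persons and unequal denominators.** Suppose 50 of 100 eligible patients enrol and all 50 end in triads, so the triad rate is 50.0%.

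- With 5 of 10 interpreters and 8 of 40 providers, the pooled rate is (50 + 5 + 8)/(100 + 10 + 40) = 63/150 = 42.0%, below the triad rate.
- With 45 of 50 interpreters and 18 of 20 providers, it is (50 + 45 + 18)/(100 + 50 + 20) = 113/170 = 66.5%, above it.

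So the sign of any enrolment bias depends on counts the protocol does not give. Steering willing interpreters to consenting patients does not settle it either: that allocates people who have already agreed and does not raise the share of eligible interpreters who agree.

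**The case for a change.** The strongest case for a change is that who is counted, and what completion means, is the substance of a primary outcome rather than an analysis detail. The protocol states the outcome in its table instead of deferring it. The debriefing that could reverse the retention bias is placed after study completion, so on the plain wording it lies outside retention, and pooling would then inflate the rate. The patient-only reading is not a full answer either: a consenting patient whose provider declines, or who has no eligible interpreter, yields no triad, so patient consent is only an upper limit on triad yield.

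Much of this is fair. The word is used in both senses, pooled retention would flatter the study if interpreters and providers complete at the visit, and triad yield is the more useful planning figure. But the case needs a pooled rule, and the protocol contains none. It recruits the roles by separate routes, which points to reporting by role. It must count complete triads anyway, since the target is 50 of them, and the research assistant is to record difficulties with clinic appointments. Nor is a visit without all three roles worthless: pain relief and interference are patient reports, and the table's row for the Mutual Understanding Scale describes only patient and provider questions.

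**Conclusion.** The claim that the stated rule overstates both rates is not established. For retention it holds only if roles are pooled and interpreters and providers nearly all complete; with 50 people per role and an assumed 60% to 80% of patients completing, the pooled figure would be 86.7% to 93.3%. If participants means patients, the difference is zero. For enrolment the direction is open, as 42.0% and 66.5% against the same 50.0% show. No size of bias can be derived from the protocol.

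What survives is missing detail on unit, denominator and completion. These are descriptive rates with no threshold or progression rule, so no decision in the document turns on the choice. A competent analyst would report enrolment and completion by role, with the count of complete triads beside them, and a SAP, not at hand here, is the usual place to say so. This is a gap that is sensibly filled at analysis, and the plan need not change.

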- 3) Pain interference will be measured using a one-item question derived from the 12-Item Short-Form Health Survey (SF-12): "During the past 4 weeks, how much did pain interfere with your normal work including both work outside the home and housework?" This will have five Likert response categories: "not at all," "a little bit," "moderately," "quite a bit," or "extremely." We translated and tested this item in Hmong in our previous research.
- 4) Satisfaction with communication will be measured using one item--"Overall, how satisfied are you with your doctor's communication with you about pain?" with response categories of very satisfied, satisfied, neither satisfied nor dissatisfied, dissatisfied, or very dissatisfied.
- 5) Quality of communication will be measured using one item--"Overall, how would you rate this doctor's communication about pain with you? " with response items of excellent, very good, good, fair, or poor. This question was modeled after the Quality of Communication Questionnaire (Engelberg, Downey, & Curtis, 2006)
- 6) Debriefing interviews will assess additional information not captured by the outcome measures including exploring the ability of the outcome measures to capture participant

experiences (conceptualization mechanism) related to MU, satisfaction with communication, pain diagnosis and treatments, and pain relief and interference. As part of the pilot test, we will also conduct a debriefing interview with the interpreters to better understand their experience and how we can better implement the tool in future studies.

The time it takes to complete the survey and interviews will vary from 10 to 30 minutes for patients, interpreters, and providers. All survey and interview completion will be conducted in a private area.

Face-to-face research activities will be conducted according to institutional policy at the time in-person visits begin.

Research Procedures:

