Primary	Mutual Understanding Scale – Main Symptom Item	Immediately post usual care / intervention	One question item from the 6-item MUS asks patients about their main symptom (i.e., “What was the most important health compliant for which the physician was visited?”) and providers to report patients’ main symptom (e.g., “What was the most important health complaint for which the patient consulted with you?”).
Secondary	Visit-Specific Satisfaction Questionnaire (VSQ)- Satisfaction with communication item	Immediately post usual care/intervention	Four items of satisfaction of the VSQ subscale related to explanations of health management (i.e., “In terms of your satisfaction, how would you rate the explanation of what was done for you”, information about the outcome (i.e., “In terms of your satisfaction, how would you rate the information about the outcome [diagnosis, treatment options,

			activity participation]; interpersonal care (i.e., In terms of your satisfaction, how would you rate the personal manner [courtesy, respect, sensitivity, friendliness] of the provider), and general satisfaction (In terms of satisfaction, how would you rate the visit overall?).
Secondary	Pain relief	Four weeks post usual care / intervention	Patients will be asked to rate the amount of their pain relief experienced since the clinic visit using a 5-point Verbal Rating Scale: none, slight, moderate, lots, complete.
Secondary	Pain interference	Immediately and 4 weeks post usual care/intervention	One question item derived from the 12-Item Short-Form Health Survey: "During the past 4 weeks, how much did pain interfere with your normal work including both work outside the home and housework?" with response options: "not at all," "a little bit," "moderately," "quite a bit," or "extremely."

Data Protection Plan:

To address the risk of loss of confidentiality and privacy, there will be no identifiers in the transcripts, surveys, and datasheets. Specifically, each study participant will receive a code number to which all study data will be linked. The code will be known only by the PI

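### Pain interference asked immediately after the visit is listed as an outcome, but its 4-week recall describes the period before the visit

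*Protocol*

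**What the plan says.** The Outcome Measures table of the protocol lists pain interference as a secondary outcome with the time frame "Immediately and 4 weeks post usual care/intervention". The item given there is "During the past 4 weeks, how much did pain interfere with your normal work including both work outside the home and housework", with five response categories. Item 3 of the measures list under Study Procedures and Interventions gives the same question. Neither place has a version with a shorter recall for the first reading.

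Research Procedures, step 4 (Post-Visit), sets the first reading straight after the consultation: "Patients in both the usual care and intervention conditions will also orally report their pain interference to the RA". By then, patients in the intervention phase have already used the tool. Step 2 has the interpreter and "patient to complete the pain assessment InfoViz tool together in the waiting area", and step 3 has the interpreter use it during the visit. The second reading is taken by telephone, which step 4 times as "Within 4 weeks of the clinic visit".

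Nothing in the protocol calls the immediate reading a baseline or describes a separate interference measurement before the visit. Pain relief, in the neighbouring row of the table, is anchored to the visit and asked only at four weeks.

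**The concern.** An outcome time point should be one at which the exposure could have changed the quantity measured. The immediate time frame suits mutual understanding and satisfaction, because those items concern the visit just finished. It does not suit an item that looks back 4 weeks: interference with work over that period had already happened when the tool was first used.

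Aim c is to evaluate the chosen outcome measures, pain interference among them, and the pilot is meant to identify changes to outcome variables for a larger efficacy study. With the immediate reading listed as an outcome, two misreadings become possible. A difference between conditions could be taken for benefit or harm from the tool, and a null result could be held against the item although it had no opportunity to show an effect.

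The first risk is greater because the protocol describes a usual care phase and an intervention phase with no stated randomisation, so no stated design feature balances patients' starting levels. Eligibility asks only for self-reported pain, without limits on severity or duration, so those levels may vary widely.

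**Working it through.** The plan gives no figure to reproduce on this point. The check is how much of the recall window falls after the visit.

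**Inputs**
- Recall window: 4 weeks = 28 days (Outcome Measures table; Study Procedures and Interventions, item 3).
- First reading: immediately after the visit, d = 0 (Research Procedures, step 4).
- Start of exposure: the same day, in the waiting area (step 2).
- Second reading: 4 weeks after the visit in the table, but within 4 weeks in step 4. Taking 4 weeks as 28 days, d = 28 under the table and at most 28 under step 4.

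**Formula.** With d the number of days from visit to interview, the share of the recall window after the visit is min(d, 28) / 28.

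| Interview day d | Recall days after the visit | Share |
|---|---|---|
| 0 (immediate reading) | 0 of 28 | 0% |
| 7 (assumed) | 7 of 28 | 25% |
| 14 (assumed) | 14 of 28 | 50% |
| 21 (assumed) | 21 of 28 | 75% |
| 28 (table's time frame) | 28 of 28 | 100% |

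Days 7, 14 and 21 are assumptions that illustrate what step 4 permits; the protocol gives no distribution of call days.

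At d = 0, apart from the hours of the visit day itself, the whole window precedes the tool and any treatment that follows from it. This holds whenever the later call is made. The later reading is clear of pre-visit time only at day 28 or beyond.

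**The case against.** The strongest reply is that the table merely lists when a repeated item is collected. On that view the two readings form a before-and-after pair, and the outcome is the change. The protocol has no analysis section, the SAP is not shown, and covariate adjustment is commonly left to a SAP. Part of this stands: a pair is the sensible use of the data, and the SAP may already use them so. But the table names both times as time frames of a secondary outcome and does not mention change or baseline, so the label still needs correcting.

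Three stronger readings are tempting, and the documents do not support them.

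- *The immediate answer cannot respond to the tool at all, so any difference must be baseline imbalance.* Past interference cannot change, but the answer is spoken after the tool and the visit. A tool meant to change how pain is expressed could also shift how past interference is reported. The reading is a baseline in content, not a clean pre-exposure measurement, and adjusting for it could absorb part of such a shift.
- *The plan fails to use this value as a baseline and ignores where patients started.* The protocol only fails to designate it as one. Its use in analysis cannot be known without the SAP.
- *The 4-week reading is wholly post-visit.* That is true for a call at day 28 or later, and step 4 allows earlier calls.

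It is also fair to say that debriefing interviews will explore whether the measures capture participants' experience. A null at the immediate time point would therefore not be the only evidence on the item.

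**Conclusion.** The point holds as a mismatch between an item's recall period and one of its two stated outcome time points. About 0 of the 28 recall days at the immediate reading follow the visit. It therefore cannot measure an effect on interference, and a difference between conditions there would mainly reflect pre-existing differences, chance or altered reporting.

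This rests on the item being asked at the clinic with the wording shown, which both places in the protocol confirm. It does not depend on the sample size or on any analysis method.

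The impact is modest. No primary outcome is affected and no data are lost. The table should be corrected because the pilot's purpose includes choosing outcomes for a larger study.

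**What to change.** In the Outcome Measures table:

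1. Make 4 weeks after usual care or intervention the only outcome time point for pain interference.
2. Relabel the first reading as *pain interference over the 4 weeks before the visit (collected immediately post-visit)*.
3. Report the 4-week value as change from, or adjusted for, that reading. State beside it that the reading is collected after exposure, so it is a baseline in content but its reporting may have been affected by the tool or the visit.
4. Reconcile the call timing in Research Procedures, step 4, with the time frame in the table. Recording the day of each call would show how much of each recall window follows the visit.

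The cost is a change of wording in one table row and in the call-timing text, and one baseline term in the analysis if the SAP does not already have it. No new visit or question is needed. One listed outcome time point is given up, and it could not have shown an effect on interference.
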